8 STUDY OBJECTIVES

The objectives of the study are as follows:

Primary Efficacy Objective:

- To evaluate the effect of sarizotan (high dose), compared to placebo, on reducing the number of apnea episodes, during awake time, in patients with RTT with respiratory abnormalities.

Key Secondary Efficacy Objective:

- To evaluate the effect of sarizotan (high dose), compared to placebo, on the Caregiver-rated Impression of Change (CIC) from baseline;

Secondary Objectives:

[figure not shown]
- Safety: To evaluate the safety and tolerability of sarizotan in patients with Rett syndrome (RTT) with respiratory abnormalities.
- Efficacy: To evaluate the efficacy of the dose range of sarizotan, compared to placebo, on the following:
 - Severity of patient symptoms, based on evaluation of Caregiver Top 3 Concerns (Visual Analogue Scale [VAS]);
 - Global change from baseline, assessed by the Clinical Global Impression of Change (CGI-C);
 - Motor behavior, assessed by the Motor-Behavioral Assessment Scale;
 - Other respiratory symptoms of Rett syndrome, assessed during awake time, including:
 - Percent time spent with breathing dysrhythmia (% time apnea + % time hyperventilation) per hour;
 - Number of hyperventilation episodes (≥ 10 seconds each) per hour;
 - Oxygen saturation (number of episodes of oxygen desaturation below 90% per hour).
 - *Respiratory Distress Index* - The sum of the following parameters calculated per hour of wakefulness: 1) number of breath-holding episodes, 2) number of episodes of hyperventilation [1 and 2 are as defined in inclusion criteria; each would have to be ≥ 10 seconds in duration], and 3) number of drops in oxygen values to $< 90\%$.
 - Overall assessment of symptoms of RTT using the Rett syndrome Clinical Severity Scale (RCSS).
 - To determine the efficacy of sarizotan in patients who attain a minimum plasma exposure of 400 ng/ml on Day 15 (expected efficacious concentration based on the knockout mouse model);
- To determine the pharmacokinetic profile of sarizotan at the doses tested and compare with the pharmacokinetic profile in adults.

9 INVESTIGATIONAL PLAN

9.1 Study Design

This is a prospective, 24-week, randomized, double-blind, placebo-controlled study designed to evaluate the safety, tolerability, and efficacy of multiple oral doses of sarizotan in patients with RTT with respiratory abnormalities. At least 129 patients will be randomized (approximately 43/group) to receive either low dose sarizotan (2 mg *bid* or 5 mg *bid*), high dose sarizotan (5 mg *bid* or 10 mg *bid*) or placebo *bid*. Patients 4 to <13 years of age will be randomized equally (1:1:1) to sarizotan 2 mg *bid* (low dose group), sarizotan 5 mg *bid* (high dose group), or placebo. Patients ≥ 13 years of age and weighing ≥ 25 kg will be randomized equally (1:1:1) to sarizotan 5 mg *bid* (low dose group), sarizotan 10 mg *bid* (high dose group), or placebo [Note: patients ≥ 13 years of age and weighing <25 kg will be eligible for the study, but will be included with the younger patients and randomized equally (1:1:1) to sarizotan 2 mg *bid* (low dose), sarizotan 5 mg *bid* (high dose) or placebo]. The paradigm for randomizing patients based on age and weight criteria is summarized schematically in Figure 4.

Figure 4. Randomization of patients to treatment according to age and body weight criteria

All patients 4 to <13 years of age, as well as those ≥ 13 years of age and weighing <25 kg, randomized to sarizotan 2 or 5 mg *bid* will start at a single dose of 2 mg on the morning of Day 1. Patients assigned to the 2 mg *bid* dose will remain on 2 mg once daily on Days 2-7, and will have their dose increased to 2 mg *bid* on Days 8-14. Patients assigned to the 5 mg *bid* dose will have their daily dose of sarizotan increased to 4 mg (2 mg *bid*) on Days 2-7, 7 mg (5 mg AM, 2 mg PM) on Day 8, and 10 mg (5 mg *bid*) on Days 9-14. Patients ≥ 13 years of age and weighing ≥ 25 kg randomized to sarizotan 5 or 10 mg *bid* will start at a single dose of 5 mg on the morning of Day 1, with an increase to 5 mg *bid* on Day 2. Patients randomized to 5 mg *bid* will continue on this dose for the rest of the study, while patients randomized to 10 mg *bid* will receive a single dose of 10 mg on Day 8 and have their dose increased to 10 mg *bid* on Day 9, and continue

on this dose. If patients do not tolerate the proposed titration and target dose, the investigator will provide only one of the two daily doses (e.g. 5 mg/day) for a few days prior to reinitiating the intended *bid* dose (e.g. 5 mg *bid*). If the dose is still not tolerated, a reduction to a lower rescue dose will be permitted. Dose titration should be completed by Day 14, after which patients will continue on their maximum tolerated dose (MTD) through the final dose, unless intolerance develops, and a dose reduction is warranted. Patients will return for scheduled visits at Weeks 8, 16 and 24, at which time efficacy and safety assessments will be performed.

All patients, including those randomized to placebo, who have completed the final evaluations at Week 24 (Day 168), have no safety or tolerability issues that would preclude continuing on the study medication, have been compliant with the trial requirements, and have not worsened to the extent that they are considered at an increased risk for morbidity or mortality, as judged by the Investigator, will have the option of continuing open-label treatment with sarizotan for an additional 24 weeks. Patients who are judged to be benefitting from treatment with sarizotan, and are not experiencing significant adverse events, will be eligible for an additional 144 weeks of open-label treatment.

The final safety and efficacy evaluations performed at Week 24 will serve as the baseline assessments for this open-label extension period. All patients meeting the inclusion/exclusion criteria, including those previously randomized to placebo, will receive treatment with sarizotan, and will start at a dose of 2 mg *bid* (patients <13 year of age and patients ≥ 13 years of age weighing <25 kg) or 5 mg *bid* (patients ≥ 13 years of age weighing ≥ 25 kg). Patients will have their dose maintained at 2 mg *bid* (patients <13 year of age weighing 10 to <18 kg), increased to 5 mg *bid* (patients <13 year of age weighing ≥ 18 kg and patients ≥ 13 years of age weighing <25 kg), or increased to 10 mg *bid* (patients ≥ 13 years of age weighing ≥ 25 kg) at Week 28, if there are no tolerability issues, and will continue on this dose. Patients will return for scheduled visits at Weeks 32, 40 and 48, in the initial open-label period, and Weeks 60, 72, 84, 96, 108, 120, 132, 144, 156, 168, 180 and 192, if they continue open-label treatment, at which time efficacy and safety assessments will be performed. A Safety Follow-up visit will be performed two weeks after the last dose of study medication.

An overview of the study design for the initial 24-week double-blind treatment period, the initial 24-week open-label extension treatment period, and Parts 1, 2 and 3 of the additional 144-week extension treatment period is provided in [Table 1](#), and [Tables 2A, 2B, 2C, and 2D](#), respectively.

Amend. 1, 19Jan2016; Amend. 2, 18May2016; Amend. 3, 21Oct2016; Amend. 4, 03Mar2017; Amend. 5, 29Mar2017; Amend. 6, 13Apr2017; Amend. 7, 02Oct2017; Amend. 8, 02Nov2017; Amend. 9, 11Feb2018; Amend. 10, 29Nov2018; Amend. 13, 10Dec2019; Amendment 14, 17 March 2020, Clean, Final

Table 1. Summary of Study Design: Initial 24-Week, Double-blind, Treatment Period

Period	Screening	Baseline	Randomized Treatment Period				Final Evaluation	Safety follow-up
Study Day(s)/ Week	-28 to -1	Days 0 and 1 (pre-dose)	Days 1 and 2	Days 14 and 15	Week 8	Week 16	Week 24 (or early d/c)	2 weeks after last dose
Duration	28 days	1 day	2 days	2 days	1 day	1 day	1 day	1 day
Treatment/Procedures	Informed consent; Screening evaluations; home respiratory monitoring (on 3 days in each of the first 3 weeks); I/E criteria assessed	Hospital visit; Baseline safety and efficacy assessments; confirm patient still meets I/E criteria; randomization	First 3 doses in hospital setting; dose titration, PK sampling and safety assessments; return home on Day 2	Hospital visit; dose titration complete (telephone contact on Day 7); home respiratory monitoring on 3 days in the week prior to visit; PK sampling, and safety and efficacy assessments	Home respiratory monitoring on 3 days in the week prior to visit; all safety and efficacy assessments	Home respiratory monitoring on 3 days in the week prior to visit; all safety and efficacy assessments	Home respiratory monitoring on 3 days in the week prior to visit; all safety and efficacy assessments	Vital signs and adverse events for patients not continuing treatment in the open-label extension period

Table 2A. Summary of Study Design: Open-Label Extension Treatment Period (Weeks 24 – 48)

Period	Baseline (extension)	Initial Open-Label Treatment Period						Safety follow-up
Study Week	Week 24	Week 25	Week 28	Week 29	Week 32	Week 40	Week 48 (or early d/c)	2 weeks after last dose*
Duration	1 day	1 day	1 day	1 day	1 day	1 day	1 day	1 day
Treatment/Procedures	Informed consent; Week 24 safety and efficacy assessments from initial period will serve as baseline for extension; confirm patient is eligible to continue treatment; all patients start re-titration with sarizotan 5 mg bid on same day #	Telephone contact on Day 175 to confirm tolerability of dose; assess AEs and conc. medication	Selected safety and efficacy assessments; dose increase to 10 mg bid , if no tolerability issues	Telephone contact on Day 203 to confirm tolerability of dose; assess AEs and conc. medication	Selected safety and efficacy assessments	Selected safety and efficacy assessments	All safety and efficacy assessments; this will be the final evaluation for patients not continuing open-label treatment	Vital signs and adverse events for all patients

Additional procedures and administration of the first dose of study medication in the open-label extension period should be performed on the same day as the Week 24 final assessments from the double-blind period, if possible.

*To be performed for patients who discontinue prematurely and those not continuing open-label treatment.

Amend. 1, 19Jan2016; Amend. 2, 18May2016; Amend. 3, 21Oct2016; Amend. 4, 03Mar2017; Amend. 5, 29Mar2017; Amend. 6, 13Apr2017; Amend. 7, 02Oct2017; Amend. 8, 02Nov2017; Amend. 9, 11Feb2018; Amend. 10, 29Nov2018; Amend. 13, 10Dec2019; Amendment 14, 17 March 2020, Clean, Final

Table 2B. Summary of Study Design: Open-Label Extension Treatment Period (Weeks 49 - 96)

Period	Additional Open-Label Treatment Period (Part 1)*							Final (#) Evaluation	Safety follow-up
Study Week	Week 54	Week 60	Week 66	Week 72	Week 78	Week 84	Week 90	Week 96 (or early d/c)	2 weeks after last dose
Duration	1 day	1 day	1 day	1 day	1 day	1 day	1 day	1 day	1 day
Treatment/ Procedures	Telephone contact to assess AEs, conc. medication and compliance with study medication	Selected safety and efficacy assessments	Telephone contact to assess AEs, conc. medication and compliance with study medication	All safety and efficacy assessments	Telephone contact to assess AEs, conc. medication and compliance with study medication	Selected safety and efficacy assessments	Telephone contact to assess AEs, conc. medication and compliance with study medication	All safety and efficacy assessments	Vital signs and adverse events for all patients

*Only those patients who have completed 24 weeks of open-label treatment, and at the Week 48 visit are judged by the Investigator to be benefitting from treatment, are not experiencing significant adverse events, and for whom informed consent has been provided, will be eligible to continue open-label treatment in this period of the study.

The Week 96 evaluation will be the final assessment for patients in Part 1 who are not continuing in Part 2 of the additional open-label extension treatment period (Weeks 97-144).

Table 2C. Summary of Study Design: Open-Label Extension Treatment Period (Weeks 97 - 144)

Period	Additional Open-Label Treatment Period (Part 2)*							Final (#) Evaluation	Safety follow-up
Study Week	Week 102	Week 108	Week 114	Week 120	Week 126	Week 132	Week 138	Week 144 (or early d/c)	2 weeks after last dose
Duration	1 day	1 day	1 day	1 day	1 day	1 day	1 day	1 day	1 day
Treatment/ Procedures	Telephone contact to assess AEs, conc. medication and compliance with study medication	Selected safety and efficacy assessments	Telephone contact to assess AEs, conc. medication and compliance with study medication	All safety and efficacy assessments	Telephone contact to assess AEs, conc. medication and compliance with study medication	Selected safety and efficacy assessments	Telephone contact to assess AEs, conc. medication and compliance with study medication	All safety and efficacy assessments	Vital signs and adverse events for all patients

*Only those patients who have completed 72 weeks of open-label treatment, and at the Week 96 visit are judged by the Investigator to be benefitting from treatment, are not experiencing significant adverse events, and for whom informed consent has been provided, will be eligible to continue open-label treatment in this period of the study.

The Week 144 evaluation will be the final assessment for patients in Part 2 who are not continuing in Part 3 of the additional open-label extension treatment period (Weeks 145-192).

Table 2D. Summary of Study Design: Open-Label Extension Treatment Period (Weeks 145 - 192)

Period	Additional Open-Label Treatment Period (Part 3)*							Final Evaluation	Safety follow-up
Study Week	Week 150	Week 156	Week 162	Week 168	Week 174	Week 180	Week 186	Week 192 (or early d/c)	2 weeks after last dose
Duration	1 day	1 day	1 day	1 day	1 day	1 day	1 day	1 day	1 day
Treatment/ Procedures	Telephone contact to assess AEs, conc. medication and compliance with study medication	Selected safety and efficacy assessments	Telephone contact to assess AEs, conc. medication and compliance with study medication	All safety and efficacy assessments	Telephone contact to assess AEs, conc. medication and compliance with study medication	Selected safety and efficacy assessments	Telephone contact to assess AEs, conc. medication and compliance with study medication	All safety and efficacy assessments	Vital signs and adverse events for all patients

*Only those patients who have completed 120 weeks of open-label treatment, and at the Week 144 visit are judged by the Investigator to be benefitting from treatment, are not experiencing significant adverse events, and for whom informed consent has been provided, will be eligible to continue open-label treatment in this period of the study.

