The final evaluations performed at Week 24 in the double-blind period, including assessments of respiratory function performed in the clinic using a stretch-sensitive resistance plethysmograph (SOMNOtouch), vital signs (body weight, height, temperature, respiratory rate, pulse, and systolic and diastolic blood pressure), laboratory tests (hematology, biochemistry, urinalysis, serum prolactin, plasma ACTH and cortisol, serum pregnancy test for post-pubertal females), ECG, physical and neurological examinations, Tanner Staging, routine ophthalmological examination [including Optical Coherence Tomography (OCT), if feasible] and final assessments for other efficacy variables [Motor-Behavioral Assessment Scale, Caregiver Top 3 Concerns, and Rett syndrome Clinical Severity Scale (RCSS)] will serve as the baseline assessments for the open-label extension period. Once all of these Week 24 assessments have been completed, and the consent form for the extension period has been signed, patients meeting all entry criteria will start on the low dose (5 mg *bid*) of sarizotan.

The first dose of the extension period (2 or 5 mg sarizotan) should be administered in the clinic (if the morning dose was given, wait at least 6 hours after the prior dose before administration) on the same day (Day 168); however, if necessary, it can be postponed until the following morning. Patients will be observed for the occurrence of any adverse events in the initial 4-hour period after the first dose. Safety evaluations (vital signs, 12-lead ECG, physical and neurological examinations) will be performed at 1 and 4 hr- post-dose. If no significant side effects are noted within the 4-hr period following the first dose, the patient will be released from the hospital and given a supply of study medication for the remainder of the first four weeks of dosing at 2 or 5 mg *bid*.

The patient/caregiver will receive a telephone contact from the Investigator/site staff on Days 175 (Week 25) to inquire about the tolerability of the current dose of the study medication. If there are no tolerability issues, the patient/caregiver will be instructed to continue on the current dose. If intolerance develops, a reduction to 2 or 5 mg once daily can be instituted, or if necessary, the patient can be asked to return to the clinic for an unscheduled visit for a full assessment.

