3	Placebo	8:00 AM	1 x Pbo	6 x Pbo	1 x Pbo	6 x Pbo	7 x Pbo
		8:00 PM	1 x Pbo	6 x Pbo	1 x Pbo	6 x Pbo	7 x Pbo

Each bottle for the 14-day titration period will contain one extra capsule in case of loss or damage.

*Number of capsules supplied for each week of dosing; patient will continue at maximum tolerated dose (MTD).

Each of the 2-week kits dispensed during this maintenance period will have 2 extra capsules in each bottle in case of loss or damage.

Abbreviations: Pbo = Placebo; Sar = Sarizotan

Packaging for the 168-week open-label extension treatment period will consist of 2-bottle kits containing enough medication (2-mg, 5-mg or 10-mg sarizotan capsules) for 2 weeks of dosing plus 2 extra capsules (16 capsules total). The dose strength will be pre-printed on the labels on the boxes for the 2-bottle kits, as well as on the individual bottles. Multiple kits will be supplied to cover the period of dosing prior to the next scheduled visit. Study medication dispensing for the open-label period by visit is presented in [Tables 4A](#) and [4B](#).

Table 4A. Study Medication Dispensing by Visit and Age/Body Weight Category: Initial Open-Label Extension Period (Weeks 24 - 40)

Study Week (Day)	Age / Body Wt. Category	Dose Type	Sarizotan Daily Dose	Dosing Period	No. of Two-Bottle Kits (Bottles) Dispensed ^s	Total No. of Capsules Dispensed
Week 24 (Day 168)	<13 yr / ≥10 kg, or ≥13 yr / <25 kg	Starting	2 mg bid	4 weeks	2 (4)	64
		Starting	5 mg bid	4 weeks	2 (4)	64
Week 28 (Day 196)	<13 yr / ≥10 to <18 kg	Target	2 mg bid	4 weeks	2 (4)	64
		Drop-back (od dosing) #	2 mg od	4 weeks	1 (2)	32
	<13 yr / ≥18 kg, or ≥13 yr / <25 kg	Target	5 mg bid	4 weeks	2 (4)	64
		Drop-back *	2 mg bid	4 weeks	2 (4)	64
		Drop-back (od dosing) #	2 mg od	4 weeks	1 (2)	32
	≥13 yr / ≥25 kg	Target	10 mg bid	4 weeks	2 (4)	64
		Drop-back *	5 mg bid	4 weeks	2 (4)	64
Drop-back (od dosing) #		5 mg od	4 weeks	1 (2)	32	
Weeks 32 & 40 (Days 224 & 280)	<13 yr / ≥10 to <18 kg	Target	2 mg bid	8 weeks	4 (8)	128
		Drop-back (od dosing) #	2 mg od	8 weeks	2 (4)	64
	<13 yr / ≥18 kg, or ≥13 yr / <25 kg	Target	5 mg bid	8 weeks	4 (8)	128
		Drop-back *	2 mg bid	8 weeks	4 (8)	128
		Drop-back (od dosing) #	2 mg od	8 weeks	2 (4)	64
	≥13 yr / ≥25 kg	Target	10 mg bid	8 weeks	4 (8)	128
		Drop-back *	5 mg bid	8 weeks	4 (8)	128

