All patients, including those randomized to placebo, who have completed the final evaluations at Week 24 (Day 168), have no safety or tolerability issues that would preclude continuing on the study medication, have been compliant with the trial requirements, and have not worsened to the extent that they are considered at an increased risk for morbidity or mortality, as judged by the Investigator, will have the option of continuing open-label treatment with sarizotan for 24 weeks. Each patient's parent, legal guardian, or representative, must provide written informed consent prior to the patient's participation in this initial

Amend. 1, 19Jan2016; Amend. 2, 18May2016; Amend. 3, 21Oct2016; Amend. 4, 03Mar2017; Amend. 5, 29Mar2017; Amend. 6, 13Apr2017; Amend. 7, 02Oct2017; Amend. 8, 02Nov2017; Amend. 9, 11Feb2018; Amend. 10, 29Nov2018; Amend. 13, 10Dec2019; Amendment 14, 17 March 2020, Clean, Final

extension period. The patient should provide assent, if capable of doing so. At the end of the initial 24 weeks of open-label treatment, the Investigator will make a global assessment of the patient. If in the Investigator's opinion, the patient is benefitting from treatment with sarizotan and is not experiencing any significant adverse events, they will be eligible to continue open-label treatment. Informed consent must be obtained at Week 48, for the patient to continue open-label treatment for an additional 48 weeks (through Week 96), again at Week 96 for the patient to continue open-label treatment for another 48 weeks (through Week 144), and again at Week 144 for the patient to continue open-label treatment for another 48 weeks (through Week 192).

At Week 24 (Day 168), all patients ≥ 13 years of age and weighing ≥ 25 kg, including those originally randomized to placebo and those receiving 5 mg once daily, will receive treatment with sarizotan, and will start at a dose of 5 mg *bid*. Patients 4 to < 13 years of age and patients ≥ 13 years of age but weighing < 25 kg, including those who were randomized to placebo, will receive sarizotan at a starting dose of 2 mg *bid*. If patients do not tolerate this starting dose, the Investigator will instruct the caregiver to administer only the morning dose (i.e. 2 or 5 mg once daily) for a few days prior to reinitiating the intended *bid* dose (i.e. 2 or 5 mg *bid*). If the 2 or 5 mg *bid* dose is still not tolerated, a reduction to 2 or 5 mg once daily will be permitted.

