- ^C Safety follow-up to be performed 14 days after the final dose of study medication in the extension treatment period, or if the patient discontinues prematurely.
- ^D Recording of dosing for the final dosing period.
- ^E Patients will be contacted 30 days after their final dose of study medication to follow up on the occurrence of any SAEs.
- ^F Patients will undergo cardiorespiratory monitoring in the clinic at each scheduled visit using a specialized data acquisition system (SOMNOtouch).
- ^G Telephone contact with patient/caregiver will be done on Days 175 and 203 (± 1 day), and at Weeks 54, 66, 78, 90, 102, 114, 126, 138, 150, 162, 174 and 186 (± 1 week), to assess tolerability of the current dose of study medication; adverse events and concomitant medication use will be assessed.
- ^H Patients completing 336 days (± 14 days) of treatment will be considered to have completed the initial 24-week extension treatment period of the study.
- ^I On Day 168 (first dose at 5 mg bid) and Day 196 (first dose at 10 mg bid), vital signs, ECG and physical/neurological examinations will be performed pre-dose and 1 and 4 hr post-dose. At Baseline (Day 168), assessments performed as part of the final Week 24 evaluations in the preceding double-blind period of the study will serve as the pre-dose assessment.
- ^J To be performed for all post-pubertal females.
- ^K Ratings of the CGI-C and CIC for the open-label extension period should be based on the patient's condition at the Week 24 visit.
- ^L The first dose (5 mg) at the starting dose (5 mg *bid*) on Day 168 (Week 24) and the first dose (10 mg) at the target dose (10 mg *bid*) on Day 196 (Week 28) will be administered in the clinic at least 6 hours after the previous dose.
- ^M Informed consent must be obtained at Week 48, at Week 96, and again at Week 144, for the patient to continue open-label treatment for an additional 48 weeks. If in the Investigator's opinion, the patient is benefitting from treatment with sarizotan and is not experiencing any significant adverse events, they will be eligible to continue open-label treatment.
- ^N All Week 96 (Final) evaluations should be performed for subjects who complete Part 1 of the additional open-label treatment period and do not continue open-label treatment, or when a subject discontinues from the study prematurely after Week 48 and prior to Week 96.

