11.4.12 Week 24 (Day 168) – Baseline for open-label extension period

- a) Obtaining written informed consent for the initial 24-week open-label extension treatment period;
- b) Assessment of inclusion/exclusion criteria for the extension treatment period (see [Section 9.2.7](#));
- c) Final (Week 24) evaluations for the initial double-blind treatment period will serve as the baseline evaluations for all safety and efficacy measures for the open-label extension treatment period (see [Section 11.4.10](#));
- d) First dose (2 or 5 mg) at starting dose (2 or 5 mg *bid*), dependent on age and weight, given in clinic (minimally 6 hours after last dose in double-blind period);
- e) Physical examination - at 1 and 4 hr post-dose;
- f) Neurological examination - at 1 and 4 hr post-dose;
- g) Vital signs – body weight, temperature, respiratory rate, pulse, and systolic and diastolic BP - at 1 and 4 hr post-dose;
- h) 12-lead standard ECG –at 1 and 4 hr post-dose;
- i) Adverse Events (AEs) – reported by the patient/caregiver or observed by the Investigator;
- j) Concomitant medications and significant non-drug therapies;
- k) Patient will leave hospital ~4 hours after first dose, if there are no safety issues.

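### Open-label extension dosing is stated in two conflicting ways: 5 then 10 mg bid with no age or weight limit in some places, and 2, 5 or 10 mg bid by age and weight in others

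*Protocol*

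**What the plan says.** **Statements with no age or weight limit**

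- Table 2A, Week 24 column: "all patients start re-titration with sarizotan 5 mg" *bid*. Its Week 28 column has "dose increase to 10 mg" *bid*, conditional on tolerability only. The note under the table concerns timing.
- Footnote I to Tables 6B–6E (Section 11.3): "On Day 168 (first dose at 5 mg bid) and Day 196 (first dose at 10 mg bid"). Footnote L likewise names 5 mg *bid* as the starting dose and 10 mg *bid* as the target dose.
- The Synopsis and Section 11.2 each contain a sentence that "patients meeting all entry criteria will start on the low dose", followed by 5 mg *bid* in brackets.
- Sections 12.1.2 and 12.1.3 call 10 mg *bid* the target dose without qualification.

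**Statements by age and weight**

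- Section 9.1, text: extension patients "will start at a dose of 2 mg" *bid* if they are under 13, or 13 or older and under 25 kg. Others start at 5 mg *bid*. Week 28 targets are 2, 5 or 10 mg *bid* by age and weight.
- Table 4A (Section 10.1.3): the 2 mg *bid* starting category is "<13 yr / ≥10 kg, or ≥13 yr / <25 kg". Its Week 28 targets match Section 9.1.
- Section 11.2, earlier paragraph (also in the Synopsis): the same younger or lighter patients "will receive sarizotan at a starting dose of 2 mg" *bid*.
- Section 11.4.12: "First dose (2 or 5 mg) at starting dose (2 or 5 mg" *bid*), dependent on age and weight.

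**Related gaps**

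- Sections 7.3 and 10.2 limit the 2 mg *bid* start in under-13s to 10 to under 18 kg, so they give no starting dose for under-13s of 18 kg or more.
- Section 10.1.2 lists only 5 mg and 10 mg for the open-label bottle label.

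**The concern.** These are current statements of how children are to be dosed, and they cannot all be followed. A site working from Table 2A or the Section 11.3 footnotes would start a drug-naive child from the placebo arm at 5 mg *bid*. Four weeks later it would raise a child under 13 to 10 mg *bid*. In the double-blind period Table 5 gives 10 mg *bid* only to patients aged 13 or older who weigh at least 25 kg.

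The protocol's safety argument for 10 mg *bid* does not extend to smaller children. Section 7.3 chose doses to keep predicted exposure below the rat NOAEL AUC. For patients of 10 to under 18 kg it gives that assurance at 5 mg *bid*, not at 10 mg *bid*. The QTc reassurance at 10 mg *bid* in Section 7.1.2 is likewise confined to patients of 25 kg or more.

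**Working it through.** No sample size, power or alpha figure is involved. The check sets the two rules side by side and then sizes the gap with the protocol's own exposure predictions.

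**Step 1. The two rules.**

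| Group | Start: Table 2A, footnotes | Start: 9.1, Table 4A | Week 28: Table 2A, footnotes | Week 28: 9.1, Table 4A |
|---|---|---|---|---|
| <13 y, 10 to <18 kg | 5 mg *bid* | 2 mg *bid* | 10 mg *bid* | 2 mg *bid* |
| <13 y, ≥18 kg | 5 mg *bid* | 2 mg *bid* | 10 mg *bid* | 5 mg *bid* |
| ≥13 y, <25 kg | 5 mg *bid* | 2 mg *bid* | 10 mg *bid* | 5 mg *bid* |
| ≥13 y, ≥25 kg | 5 mg *bid* | 5 mg *bid* | 10 mg *bid* | 10 mg *bid* |

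The rules agree only in the last row. According to SAP Section 1, that group was the whole population under the first protocol version, so the 5-then-10 mg wording is probably left over from then.

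**Step 2. Dose ratios, first rule over second.**

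- Start, first three rows: 5/2 = 2.5.
- Week 28, under 13 and 10 to <18 kg: 10/2 = 5.0.
- Week 28, under 13 and ≥18 kg, or ≥13 and <25 kg: 10/5 = 2.0.

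**Step 3. Exposure against the ceiling.** Inputs are from Section 7.3: predicted median steady-state AUC at 15–20 kg, and the rat NOAEL AUC of 10020 ng·h/mL.

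| Dose | Median AUC (ng·h/mL) | AUC / 10020 | 10020 / AUC |
|---|---|---|---|
| 2 mg *bid* | 1981 | 19.8% | 5.06 |
| 5 mg *bid* | 4953 | 49.4% | 2.02 |
| 10 mg *bid* | 9907 | 98.9% | 1.01 |

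The AUC ratios equal the dose ratios, as expected from the linear kinetics in Section 7.1.3 (9907/1981 = 5.0; 9907/4953 = 2.0; 4953/1981 = 2.5). What the AUCs add is the distance to the ceiling. At 10 mg *bid* the median sits almost on it, so some patients would be expected to exceed it.

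**Step 4. Below 15 kg.** The protocol gives no prediction here, although patients from 10 kg are eligible. Assume AUC is proportional to weight to the power −b.

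- Fitting b to the two weight bands in Section 7.3, at midpoints 17.5 and 50 kg: b = ln(9907/6352) / ln(50/17.5) = 0.42. At 10 kg on 10 mg *bid*: 9907 × (17.5/10)^0.42 ≈ 12,600.
- With b = 0.75, taken as an upper value: 9907 × (17.5/10)^0.75 ≈ 15,100.

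Both exceed 10020. This range is an assumption, not a protocol figure.

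**The case against.** The strongest reply is that this is leftover wording in summary text. Table 2A is presented as an overview, directly after the full age and weight rule. The footnotes mainly set the timing of assessments and of in-clinic dosing, and they name no population; only Table 2A says all patients. The sentence in the Synopsis and Section 11.2 refers to the low dose, which elsewhere means 2 or 5 mg by age and weight, and the next paragraph says 2 or 5 mg.

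The sections a site would use to dose and dispense (10.2, Tables 4A and 4B, 11.4.12, 11.4.14) follow the age and weight rule, apart from the missing starting dose in 10.2. Kits come through the IWRS with the strength pre-printed, and Table 4A has no 10 mg kit for any child under 13. First doses are given in clinic with checks at 1 and 4 hours. Because 5 mg *bid* is already the double-blind high dose for under-13s, a 5 mg *bid* start is in effect a skipped titration step. Finally, SAP Section 5.2, dated 13 days after the current protocol, describes a review of Week 24 compliance data in the past tense. Few patients may therefore have been left to enter the extension.

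Most of this stands and lowers the practical risk, but it does not remove the conflict. No precedence rule exists, and Table 2A is explicit. The IWRS description in Section 10.1.3 has the investigator enter whether the dose is increased, decreased or maintained, and states no age or weight cap. At Week 28 a child under 13 and under 18 kg should be maintained, whereas Table 2A says increase. The SAP's tense is mixed, SAP Section 3.1 says the extension is ongoing, and neither document gives the number still to enter.

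**Conclusion.** The concern holds. The current protocol carries two extension dosing rules that differ for every patient except those of at least 13 years and 25 kg. The starting-dose conflict (2.5-fold) is the lesser part. Week 28 is the substantive one: 5 times the intended dose for under-13s of 10 to under 18 kg, and twice the intended dose for under-13s of 18 kg or more and for older patients under 25 kg. The 98.9% figure applies at 15–20 kg and is a model-predicted median; the values at 10 kg rest on the scaling assumption above.

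The label text and the gap in Sections 7.3 and 10.2 are minor. In the latter, the 2 mg *bid* start can be inferred from the Week 28 increase and is stated in Table 4A. The point should be fixed for patient safety. It has no bearing on the double-blind comparison.

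**What to change.** Adopt the rule in the Section 9.1 text and Table 4A everywhere.

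- **Start:** 2 mg *bid* for all under-13s and for patients 13 or older under 25 kg; 5 mg *bid* for patients 13 or older weighing at least 25 kg.
- **Week 28:** 2 mg *bid* for under-13s of 10 to under 18 kg; 5 mg *bid* for under-13s of 18 kg or more and for patients 13 or older under 25 kg; 10 mg *bid* for patients 13 or older weighing at least 25 kg.

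Places to change:

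- Table 2A, both the Week 24 and Week 28 columns.
- Footnotes I and L to Tables 6B–6E.
- The bracketed 5 mg *bid* in the Synopsis and Section 11.2.
- Sections 7.3 and 10.2: remove the under-18 kg limit on the 2 mg *bid* start for under-13s.
- Section 10.1.2: add 2 mg to the open-label label text.
- Sections 12.1.2 and 12.1.3: refer to the target dose for age and weight instead of 10 mg *bid*.

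The cost is one clarifying amendment and a site notification. Data, analysis and sample size do not change.
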